5.3. Determination of Sample Size

Approximately 140 patients will be randomized at a 1:1 ratio in the Blinded Treatment Dosing Period (Period 2) to ixekizumab 80 mg Q4W with a starting dose 160 mg and placebo.

For 90% power to test the superiority of ixekizumab Q4W to placebo for ASAS40 at Week 16 in bDMARD-naïve patients, at least 61 patients per treatment group would be needed. The following assumptions were used for the power calculations for ASAS40 response rates: 44% for ixekizumab 80 mg Q4W treatment group and 16% for the placebo group in bDMARD naïve patients.

For the key secondary efficacy endpoint ASAS40 response at Week 16 compared to placebo group in overall study population, the power would be $>90\%$. The assumptions are 42% response rate for ixekizumab 80 mg Q4W treatment group and 15% for the placebo group in overall study population.

These assumptions are based on the review of historical clinical studies in AS (etanercept, adalimumab, infliximab, certolizumab, and golimumab [Davis et al. 2003; van der Heijde et al. 2005, 2006; Inman et al. 2008, Landewé et al. 2014]) and recent secukinumab trials including both TNF inhibitor experienced patients and naïve patients (Baeten et al. 2014b; Sieper et al. 2014).

A 2-sided Fisher's exact test at the 0.05 level is assumed. Sample size and power estimates were obtained from nQuery® Advisor 7.0.

6. A Priori Statistical Methods

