Figures showing the proportion of patients achieving a categorical clinical response at each scheduled visit within each treatment group may be provided.

Time to first clinical response (for example, ASAS40) will be assessed based on the intent-to-treat (ITT) Population in Period 2. Unless specified otherwise, time to first clinical response (for example, ASAS40) is defined as:

Time to first clinical response (days) = Date of first clinical response during Period 2 – Date of randomization + 1

If a patient has not met the criteria for response by completion or early discontinuation of Period 2, the patient will be censored at the date of their last visit during Period 2.

The number of patients at risk and experiencing a response by each scheduled visit during Period 2 will be presented by treatment group. The Kaplan-Meier estimate of the proportion of patients achieving the clinical response will be presented for each visit. Treatment group comparisons will be performed using the log-rank test and the log-rank test stratified by baseline CRP status and TNF inhibitors experienced or naïve. A Kaplan-Meier plot of the time to first clinical response by treatment group will also be provided.

Fisher's exact test will be used for all adverse event (AE), baseline, discontinuation, and other categorical safety data. Continuous vital sign and laboratory values will be analyzed by an ANCOVA with treatment and baseline value in the model.

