6.3.1. Nonresponder Imputation

Analysis of categorical efficacy and health outcome variables will be assessed using a NRI method. Patients will be considered nonresponders for the NRI analysis if they do not meet the clinical response criteria or have missing clinical response data at the primary analysis time point. All nonresponders at Week 16 (Visit 8), as well as all patients who discontinue study treatment at any time prior to Week 16 for any reason, will be defined as nonresponders for the NRI analysis at Week 16. Randomized patients without at least 1 postbaseline observation will also be defined as nonresponders for the NRI analysis.

The NRI may be applied at any time point specified for analysis.

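### Timing first response and censoring on actual visit dates inflates and destabilises the tail of the planned Kaplan-Meier curves; the size depends on inputs the plan does not give

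*SAP*

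**What the plan says.** SAP 6.1.1 defines time to first response from the "Date of first clinical response during Period 2", minus the randomisation date, plus one day. If there is no response by completion or early discontinuation of Period 2, "the patient will be censored at the date of their last visit during Period 2". The outputs are counts at risk and responding by scheduled visit, a Kaplan-Meier plot, and this: "The Kaplan-Meier estimate of the proportion of patients achieving the clinical response will be presented for each visit". On inference: "Treatment group comparisons will be performed using the log-rank test", both unstratified and stratified.

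SAP Table RHCH.6.4 applies the method to ASAS40, ASAS20, ASDAS inactive disease and ASDAS below 2.1. The Protocol Section 2 schedule collects the components at Weeks 1, 2, 4, 8, 12 and 16. Windows are ±2 days through Week 4 and ±4 days at Weeks 8, 12 and 16.

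For this analysis the SAP does not map dates to scheduled visits. It also does not state the day at which the curve is read for each visit.

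**The concern.** Response is seen only on a visit day, so the day within the window reflects scheduling and not onset of action. Up to Week 12 this does no harm, because a nonresponder who continues stays in the risk set. At Week 16 every remaining patient either responds or is censored on the day they attend. A nonresponder seen four days early is removed before a responder seen four days late, and the late responder is divided by a small remainder. Kaplan-Meier then treats the removed patient as someone who might still have responded in Period 2, although that patient's outcome is known.

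At stake are the onset-of-action displays for four endpoints. The plotted curve can end above the fraction of patients who ever responded, with an unstable last step.

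**Working it through.** **Inputs from the documents.** Arm size is 70: "Approximately 140 patients will be randomized at a 1:1 ratio" (SAP 5.3). Response rates: "The assumptions are 42% response rate for ixekizumab 80 mg Q4W treatment group and 15% for the placebo group" (SAP 5.3, overall population). The Week 16 window is day 112 ± 4. With the SAP's added day, times run from 109 to 117 and the nominal time is 113.

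**Inputs the documents do not give (assumed).** These are the share *w* of an arm first responding at Week 16, the scatter of visit dates, and drop-out. The proportion *F* ever responding is also not given; 42% and 15% stand in for it, although the SAP states them as rates at Week 16.

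**The plan's own figures.** The plan has none for this analysis. Its sample-size figures are reproduced: two-sided Fisher power is 90.5% at 61 per arm (44% v 16%), and 93.2% at 70 per arm (42% v 15%) against the stated >90%.

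**Formula.** Take no drop-out, and attendance spread evenly over the nine days regardless of response. The share at risk on entering the window is R = 1 − F + w. On the k-th day from the end, R·k/9 is still at risk and w/9 responds, so the conditional probability is (w/R)/k. Hence:

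- End of curve: 1 − R × Π(1 − (w/R)/k), k = 9 down to 1.
- Read at day 113: the same product, k = 9 down to 5.
- Scheduled-visit time: 1 − R × (1 − w/R) = F, the crude proportion.

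| F | w | R | w/R | Product to end | End of curve | Excess (points) | At day 113 |
|---|---|---|---|---|---|---|---|
| 42% | 1% | 0.59 | 0.0169 | 0.9530 | 43.8% | +1.8 | 41.7% (−0.3) |
| 42% | 3% | 0.61 | 0.0492 | 0.8685 | 47.0% | +5.0 | 41.2% (−0.8) |
| 42% | 6% | 0.64 | 0.0938 | 0.7616 | 51.3% | +9.3 | 40.4% (−1.6) |
| 15% | 2.25% | 0.8725 | 0.0258 | 0.9292 | 18.9% | +3.9 | 14.4% (−0.6) |

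Example, third row: 0.64 × 0.7616 = 0.4874, and 1 − 0.4874 = 51.3%.

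**Simulation at 70 per arm** (5% drop-out, F = 42%). Four scatters were used: 80% on the nominal day, SD 1 day, SD 2 days, and uniform. Excess is measured against Kaplan-Meier on scheduled-visit time.

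- w = 1%: +1.5 to +2.1 points; Greenwood SE ×1.08 to ×1.14; sampling SD ×1.26 to ×1.54.
- w = 6%: +8.2 to +10.7 points; Greenwood SE ×1.41 to ×1.56; sampling SD ×1.83 to ×2.36, or ×2.82 when 80% attend on the nominal day.
- All visits on the nominal day: excess 0, both ratios 1.00.

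The crude SE is √(0.42 × 0.58/70) = 0.059, so a Greenwood ratio of 1.1 to 1.5 means about 0.065 to 0.088. If more patients ever respond (60%, w = 6%), the excess is +7.3 to +9.7 points, so the result is not sensitive to using 42% for *F*.

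**Drop-out alone.** On scheduled-visit time with an assumed 10% drop-out, Kaplan-Meier gives 42.2% against a crude 40.1%, about 2 points.

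**Log-rank** (2,000 trials, uniform dates, no drop-out), day-based v scheduled-visit times. Type I error was 3.8% v 3.7% with 15% in both arms, and 4.5% v 4.8% with 42% in both. Power was 94.3% v 94.7%.

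**The case against.** The strongest reply is that the SAP promises an estimate for each visit and does not promise the last point of the curve. Read at day 113, the Week 16 figure is slightly low. That stands for the tabulated figure, but the reading day is not stated, and the plot shows the tail whichever day the table uses.

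Second, Protocol 5.4 expects maximum or near-maximum effect by Week 16, so few first responses may come that late. That also stands, and it is why the size must be conditional. A reader might infer a fixed overstatement of about 10 points and a doubled standard error. The first needs roughly 6% to 8% of an arm to respond first at Week 16, which the documents do not give. The Greenwood SE does not double in the ixekizumab-arm settings.

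A reader might also infer an exaggerated gap between arms. It widens if late first responses are proportional to each arm's response rate (+9.3 v +3.9 points above). At w = 4% in both arms the excesses are similar (+5.5 to +7.8 at 42%, +6.2 to +8.5 at 15%), so no general statement holds.

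Nor does a difference from nonresponder imputation show an error. SAP 6.3.1 treats nonresponders at Week 16, "as well as all patients who discontinue study treatment at any time prior to Week 16 for any reason, will be defined as nonresponders", but that concerns response at Week 16, which differs from ever having responded. Censoring drop-outs at the last visit is conventional and partly a matter of choice.

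Finally, SAP Section 4 lists time to first response as exploratory. It is outside the SAP 6.4 testing list, and the by-visit counts let a reader recover the crude proportion.

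**Conclusion.** The concern holds for the tail of the Kaplan-Meier curves. The stated rule inflates and destabilises it through visit scheduling alone. With 70 per arm and an assumed 42% ever responding, the excess over the crude proportion ever responding is about 1.5 points at w = 1%, about 5 at 3%, and about 8 to 10 at 6%. The Greenwood SE is about 1.1 to 1.5 times the scheduled-visit value. The sampling SD is about 1.2 to 2.2 times, and higher under some assumed scatters. At 15% ever responding, with 2.25 points first at Week 16, the excess is about 4 points. At nominal day 113 the estimate is 0 to 2 points low. All of this rests on the assumed late-response share and date scatter, and it vanishes if every Week 16 visit falls on its nominal day. The primary logistic analysis with nonresponder imputation is unaffected. No material log-rank effect has been shown. This merits a correction to the SAP but does not threaten the trial's main conclusions.

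**What to change.** In SAP 6.1.1, assign each first response to its scheduled visit (Week 1, 2, 4, 8, 12 or 16). Censor completers without a response at scheduled Week 16, after the events at that visit. Without drop-out, the Kaplan-Meier estimate at each visit then equals the proportion of randomised patients who have responded by then, and the question of which day to read disappears. Use the same times for the plot.

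Optionally, add a sensitivity display that keeps patients who stop study treatment in the risk set as nonresponders through Week 16.

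The cost is a wording change and minor programming, with no new data. Within-window day detail is lost, and the end-of-curve figures will be lower.

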5.2. Number of Participants

Participants will be screened to achieve 140 randomized participants for an estimated total of 70 evaluable participants per treatment group.

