9.2.2. Adverse Events of Special Interest

The following adverse events of special interest (AESIs) will be used to determine the safety and tolerability of ixekizumab over the range of doses selected for this clinical study.

The AESIs for ixekizumab are:

- cytopenias (leukopenia, neutropenia, and thrombocytopenia)

- clinically significant hepatic events and/or significant elevations in liver function test changes/enzyme elevations (ALT, AST, bilirubin, and alkaline phosphatase)
- infections
- injection site reactions
- allergic reactions/hypersensitivities
- cerebrocardiovascular events
- malignancies
- IBD
- interstitial lung disease
- depression.

Sites will provide details on some of these AEs as instructed on the CRF. Investigators will also educate patients and/or caregivers about the symptoms of allergic/hypersensitivity reactions and will provide instructions on dealing with these reactions (see also Section 7.7.2). A blood sample is to be collected as soon as possible for any patient who experiences an AE of a potential systemic allergic/hypersensitivity reactions during the study as judged by the investigator.

Data on preferred terms associated with cerebrocardiovascular events (defined as death, cardiac ischemic events including MI and hospitalization for unstable angina, hospitalization for heart failure, serious arrhythmia, resuscitated sudden death, cardiogenic shock, coronary revascularization procedure, stroke/transient ischemic attack, peripheral revascularization procedure, peripheral arterial event, and hospitalization for hypertension) will be collected, and these events and any deaths will be adjudicated by an external clinical events committee (CEC) made up of a chairman, 2 cardiologists, and a neurologist.

Data on suspected IBD, as identified by events possibly indicative of ulcerative colitis and Crohn's disease, will be collected and the events will be adjudicated by an external CEC with expertise in IBD.

The role of external CECs is to adjudicate defined clinical events in a blinded, consistent, and unbiased manner throughout the course of a study. The purpose of the CEC for adjudication of cerebrocardiovascular events and the CEC for adjudication of suspected IBD events is to ensure that all reported events are evaluated uniformly by a single group.

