10.3.8. Safety Analyses

Safety will be assessed by summarizing and analyzing AEs including adjudicated cerebrocardiovascular events, laboratory analytes including neutrophil counts, QIDS-SR16, C-SSRS, and vital signs. The duration of treatment exposure will also be summarized

For Period 2 (Blinded Treatment Dosing Period), safety data will be summarized for the Safety Population. Treatment group comparisons will be performed on categorical safety data using Fisher's exact test as described in Section 10.3.1; continuous safety data will be analyzed by an ANCOVA model.

For Period 3 (Extended Treatment Period), the safety data will be summarized.

For Period 4 (Post-Treatment Follow-Up Period), safety data will be summarized according to the treatment patients were on prior to entering Period 4.

The categorical safety measures will be summarized with incidence rates. The mean change of the continuous safety measures will be summarized by visits.

Further details will be described in the SAP.

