6.1. General Considerations

Statistical analysis of this study will be the responsibility of Eli Lilly and Company (hereafter Lilly). The statistical analyses will be performed using SAS® Version 9.4 or higher.

Continuous data will be summarized in terms of the number of observations, mean, standard deviation (SD), minimum, median, and maximum. The minimum and maximum will be reported to the same number of decimal places as the raw data recorded in the database. The mean and median will be reported to 1 more decimal place than the raw data recorded in the database. The SD will be reported to 2 more decimal places than the raw data recorded in the database. In general, the maximum number of decimal places reported shall be 4 for any summary statistic.

Categorical data will be summarized in terms of the number of patients in the analysis population, the number of patients providing data at the relevant time point, frequency counts, and the percentages corresponding to the appropriate method. Percentages will be presented to 1 decimal place. Percentages will not be presented for zero counts.

For continuous data, at visits of interest, change from baseline will be calculated as the observed value - the baseline value. Percent change (or percent improvement) is calculated as $100 \times \frac{\text{Baseline value} - \text{Observed value}}{\text{Baseline value}}$. If the baseline value or observed value is missing, the change from baseline and percent change (or percent improvement) from baseline will be missing.

All confidence intervals (CIs) and statistical tests will be 2-sided unless otherwise specified. P-values which are greater than or equal to 0.001, and less than or equal to 0.999, will be presented to 3 decimal places. All other p-values which are less than 0.001 will be presented as <0.001, while p-values greater than 0.999 will be presented as >0.999. Confidence intervals will be presented to 1 more decimal place than the raw data.

Age, sex, and race will be reported on all by-patient listings unless otherwise specified. Sex will be abbreviated as follows: female (F) and male (M). Race will be abbreviated as follows: Asian (AS).

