6.1.1. General Considerations for Analyses during the Blinded Treatment Dosing Period (Period 2)

Comparisons between ixekizumab regimen 80 mg Q4W and placebo will be performed for all analyses in Period 2.

Period 2 starts at the first injection of study treatment at Week 0 (Visit 2) and ends prior to the first injection of study treatment at Week 16 (Visit 8) or the ETV (between Weeks 0 and 16). If a patient has Visit 8 but does not receive injection at Week 16 (Visit 8), the last recorded time for Visit 8 is used as the end time for Period 2.

Baseline will be defined as the last available value before the first injection for efficacy, health outcome, and safety analyses. In most cases, this will be the measure recorded at Week 0 (Visit 2). For efficacy measures, if the patient does not take any injection, the last available value on or prior to randomization date will be used. Change from baseline will be calculated as the visit value of interest minus the baseline value. For safety analyses using a baseline period, the baseline period is defined as the time from Visit 1 to the date/time of the first injection.

The randomization to treatment groups is stratified by baseline CRP status (nonelevated versus elevated) and TNF inhibitors experience (experienced or naïve) as described in Section 5.2. Unless otherwise specified, the statistical analysis models will adjust for baseline CRP status, and prior TNF inhibitors experience(if applicable).

The primary analysis method for treatment comparisons of categorical efficacy and health outcomes variables at specific time points will be made using a logistic regression analysis with treatment, baseline CRP status, and TNF inhibitors experience (if applicable) in the model. The proportions, odds ratio and 95% confidence intervals (CIs) will be reported; treatment difference and 95% CIs will also be reported. Secondary analysis will be conducted using a Fisher's exact test. In the case when logistic regression model does not produce statistical results due to sparse data, Fisher's exact test will be used.

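### Period 2 adverse events of special interest get counts, percentages and a Fisher's exact test but no between-arm risk difference or confidence interval, so for the less common topics a non-significant result says little about the excess risk that remains possible

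*SAP*

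**What the plan says.** Protocol 9.2.2 lists ten AESI topics and says they "will be used to determine the safety and tolerability of ixekizumab". Protocol 10.3.8 adds for Period 2: "Treatment group comparisons will be performed on categorical safety data using Fisher's exact test". SAP 6.1.1 repeats the rule: "Fisher's exact test will be used for all adverse event (AE), baseline, discontinuation, and other categorical safety data". Table RHCH.6.7 then names Fisher's exact test for Period 2 topic by topic, including the hepatic laboratory thresholds. The exception is interstitial lung disease, which has a listing only.

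SAP 6.11.2 has the number and percentage of patients with each event shown by treatment group. Continuous laboratory values are compared by ANCOVA (SAP 6.1.1 and 6.11.4). Table RHCH.6.2 plans no between-group comparison for Period 3 or for time on ixekizumab.

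For categorical efficacy, SAP 6.1.1 asks for proportions and an odds ratio with its interval, and says "treatment difference and 95% CIs will also be reported". No equivalent sentence exists for categorical safety.

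**The concern.** A safety reading of a small trial needs to know how large an excess the data still allow. A p-value does not give that. When events are few, Fisher's exact test is also conservative and rarely reaches 0.05, so for topics such as inflammatory bowel disease, malignancy or anaphylaxis a non-significant result is likely whether or not ixekizumab raises the risk. If the p-value is the only inferential entry in the table, a reader may take it as reassurance that the data cannot give.

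**Working it through.** **Inputs.**
- Patients per arm: 70. Protocol 5.2: "Participants will be screened to achieve 140 randomized participants for an estimated total of 70 evaluable participants per treatment group". The safety population is everyone randomized and dosed at least once, so about the same number.
- Sidedness: SAP 6.1, "All confidence intervals (CIs) and statistical tests will be 2-sided unless otherwise specified".
- Level: 0.05. The documents state this for efficacy sizing only (SAP 5.3: "A 2-sided Fisher's exact test at the 0.05 level is assumed"). No safety level is given, so 0.05 is an assumption here.
- Event rates: none in the documents. Placebo risks of 1% to 25% are assumed.

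**Method.** Power = sum over all i, j from 0 to n of 1{p(i, j) ≤ 0.05} × Bin(i; n, p_ixe) × Bin(j; n, p_pbo), where p(i, j) is the 2-sided Fisher p-value.

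**The plan's own figure first.** For ASAS40 at 44% versus 16%, this gives 90.5% with 61 per arm and 89.9% with 60, so 61 is the smallest size reaching the stated 90%. For 42% versus 15% at 70 per arm it gives 93.2%, matching the stated figure of more than 90%. The method therefore reproduces the plan.

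**Smallest significant split at 70 versus 70.** For k events versus none in equal arms, p = 2 × C(70, k) / C(140, k).
- k = 4: p = 0.120
- k = 5: p = 0.058
- k = 6: p = 0.028

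An event absent on placebo must therefore occur in 6/70 = 8.6% of ixekizumab patients to reach 0.05. The 6-versus-0 threshold also held at every size checked from 61 to 80 per arm. The next smallest significant splits are 8 vs 1 (p = 0.033), 10 vs 2 (0.031) and 11 vs 3 (0.045).

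**Power at 70 per arm.**

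| Assumed placebo risk | Doubling | Tripling |
|---|---|---|
| 1% | 0.1% | 1.0% |
| 2% | 1.8% | 8.2% |
| 5% | 11.4% | 40.7% |
| 10% | 30.5% | 81.3% |
| 15% | 49.4% | 96.9% |
| 25% | 83.1% | about 100% |

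Power passes 50% at a placebo risk of about 15% for a doubling and about 6% for a tripling. It passes 80% at about 24% and about 10%.

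**What an interval would add.** Risk difference (ixekizumab minus placebo) with Miettinen-Nurminen 95% limits, 70 per arm:
- 0 vs 0: p = 1.00; -5.2 to +5.2 points.
- 3 vs 0: p = 0.245; difference 3/70 = 4.3 points, upper limit 11.9.
- 9 vs 3: p = 0.128; difference 6/70 = 8.6 points, upper limit 19.0.
- 5 vs 0: p = 0.058; difference 5/70 = 7.1 points, 1.7 to 15.7.

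The 3 vs 0 and 9 vs 3 results are both non-significant, yet they leave room for excesses of about 12 and 19 points.

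**The case against.** The best defence is that the trial was sized on ASAS40, low power for rare events is expected, and an interval displays that imprecision without curing it. All of that stands. It supports reporting the uncertainty, since no one is asking for more patients. A reader could also compute an interval from the planned counts. That is true, but the method would then be chosen after the data are seen.

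Four stronger readings are tempting, and the documents do not support them.

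- **AESIs are judged by p-values alone.** Period 2 also has counts and percentages by arm, maximum severity for several topics, hepatic shift tables and an eDISH plot, ANCOVA on laboratory values, listings, and blinded external adjudication of cerebrocardiovascular and suspected inflammatory bowel disease events. The gap is narrower: no effect estimate with an interval for categorical events.
- **The test misses most doublings and triplings whatever the topic.** This depends on the placebo risk. A tripling from 10% or a doubling from 25% is detected with more than 80% power. Infections and injection site reactions are on the AESI list and need not be rare.
- **The plan treats a non-significant result as proof of safety.** It sets no safety alpha and no decision rule, and it reports p-values to three decimals.
- **Fisher's exact test should be dropped and safety read from the upper limit.** No margin exists against which to read that limit, and adding an estimate is enough.

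Two further points stand. Table RHCH.6.7 defines cytopenias by event terms only; the laboratory grades are in SAP 6.11.4.1, which names no test. SAP 6.11.3.1 lets a program safety analysis plan (PSAP) supersede the SAP on special safety topics, and that plan was not available to check.

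**Conclusion.** The point holds as a cheap improvement to reporting. In Period 2, Fisher's exact test is the only between-arm inference specified for AESI events and the hepatic thresholds, and no risk difference or interval accompanies it. At 70 per arm the test cannot reach 0.05 below 6 versus 0. Power is under 50% for a doubling when placebo risk is below about 15%, and for a tripling when it is below about 6%. For topics in that range, a non-significant p-value barely limits the excess risk. Commoner topics may be tested adequately. The conclusion rests on about 70 treated patients per arm, a 2-sided 0.05 threshold and assumed event rates. No efficacy conclusion is affected.

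**What to change.** - In SAP 6.1.1, keep Fisher's exact test for categorical safety data. Add the Period 2 risk difference (ixekizumab minus placebo) with a 2-sided 95% confidence interval valid at zero cells, for example Miettinen-Nurminen.
- Apply this to the Period 2 AESI and hepatic-threshold tables under Table RHCH.6.7, and to the cytopenia grade categories in SAP 6.11.4.1.
- State that the intervals are descriptive, are not adjusted for multiplicity, and that p above 0.05 is not evidence of no excess risk.
- If the PSAP governs these tables, make the same change there.

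The cost is one paragraph and one column per table, with no new data. Protocol 10.3 requires an amendment only when a principal feature changes, which this does not.

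The downside is that the intervals will be wide and will sometimes disagree with the test. For 4 versus 0 the Miettinen-Nurminen interval is 0.3 to 13.8 points, which excludes zero, while Fisher's p is 0.12. The statement that the intervals are descriptive should appear with the tables for that reason.
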